Clinical Study Protocol

CCP-020 (Diacerein 1%) Topical Ointment

Sponsor Protocol No.CCP-020-103

TKL Study No. DS106217

**A Randomized, Controlled Study to Evaluate the Sensitizing
Potential of CCP-020 (Diacerein 1%) Topical Ointment in Healthy
Subjects Using a Repeat Insult Patch Test Design**

Author:

[REDACTED]

Document type: Clinical Study Protocol

Development Phase: 1

Document Date: 23-October-2017

Document Status Amendment 1

Number of Pages: 41

Property of **Castle Creek Pharmaceuticals, LLC**

Confidential

May not be used, divulged, published, or otherwise disclosed
without the consent of **Castle Creek Pharmaceuticals, LLC**

Synopsis

| | |
|--------------------------------------|--|
| Study Title: | A Randomized, Controlled Study to Evaluate the Sensitizing Potential of CCP-020 (Diacerein 1%) Topical Ointment in Healthy Subjects Using a Repeat Insult Patch Test Design |
| TKL Study Number: | DS106217 |
| Sponsor Protocol Number: | CCP-020-103 |
| Sponsor: | Castle Creek Pharmaceuticals, LLC |
| Development Phase: | 1 |
| Study Objectives: | To evaluate the sensitization potential of CCP-020 (Diacerein 1%) Topical Ointment on normal skin. |
| Study Design: | Single center, randomized, controlled, evaluator blinded, within-subject comparison study. |
| Planned Sample Size: | 200 evaluable subjects |
| Study Population: | Healthy adult males and females volunteer subjects |
| Investigational Products: | CCP-020 (Diacerein 1%) Topical Ointment, approximately 0.2 mL, applied topically under occlusive patch conditions to the infrascapular area of the back, 3 times weekly for 3 weeks (9 applications) during the Induction Phase, and one time at Challenge (10 times in total). Vehicle, approximately 0.2 mL, applied topically under occlusive patch conditions to the infrascapular area of the back, 3 times weekly for 3 weeks (9 applications) during the Induction Phase, and one time at Challenge (10 times in total). |
| Concurrent Controls: | A solution of 0.9% saline, approximately 0.2 mL applied topically under occlusive patch conditions to the infrascapular area of the back, 3 times weekly for 3 weeks (9 applications) during the Induction Phase, and one time at Challenge (10 times in total) will serve as a negative irritant control. |
| Efficacy Evaluation Criteria: | Not Applicable |

| RIPT | Repeated Insult Patch Test |
| SAE | Serious Adverse Event |
| SAP | Statistical Analysis Plan |
| SOPs | Standard Operating Procedures |
| TKL | TKL Research, Inc. |
| UPT | Urine Pregnancy Test |
| USP | United States Pharmacopeia |
| UV | Ultraviolet |

1. INTRODUCTION

This study investigates the sensitization potential of CCP-020 (Diacerein 1%) Topical Ointment under standardized conditions compared with an inert control (normal saline). Because CCP-020 (Diacerein 1%) Topical Ointment is formulated for topical use, it is necessary to determine the potential of this product to cause sensitization after repeated topical application to the skin.

The study will be conducted in compliance with Food and Drug Administration (FDA) regulations, the ethical principles of the Declaration of Helsinki concerning medical research in humans (Recommendations Guiding Physicians in Biomedical Research Involving Human Subjects, Helsinki 1964 and amendments 2013), the International Conference on Harmonization (ICH) – Good Clinical Practice (GCP) Guidelines as currently amended, and all applicable standard operating procedures (SOPs) of TKL Research, Inc. (TKL).

1.1. Background Information

CCP-020 (previously developed as AC-203) is a topical ointment containing diacerein (4,5-bis[acetoxy]-9,10-dihydro-9,10-dioxo-2-anthracene carboxylic acid; also known as diacetyl-rhein), a highly purified anthraquinone derivative, and is being developed by Castle Creek Pharmaceuticals for the treatment of epidermolysis bullosa simplex (EBS). The capsule formulation of diacerein, intended for oral use and systemic absorption, was initially approved for use in osteoarthritis (OA) in France in 1992 (as Artodar®, ART50®, or Zondar®). Since then, it has received marketing authorization in over 30 countries in Europe, South America, and Asia. It is classified as a Symptomatic Slow-Acting Drug in OA. Following oral administration of the capsule formulation, diacerein is rapidly metabolized to the deacetylated active metabolite, rhein. Similarly, diacerein in the topical formulation is hydrolyzed to rhein in the epidermis and the dermis following administration. Diacerein and rhein have been shown to inhibit the in vitro and in vivo production and activity of interleukin (IL)-1 β and other proinflammatory cytokines. It has a novel mode of action that differentiates it from non-steroidal anti-inflammatory drugs (NSAIDs) and other conventional forms of drug therapy.

For the development of CCP-020, a total of 10 animal studies have been conducted with CCP-020 ointment 1%, including one skin penetration study, three acute dermal toxicity studies, one phototoxicity study, three pharmacokinetic studies, and two sub-chronic juvenile toxicity studies. CCP-020 was well-tolerated in these studies and no untoward adverse effects (AEs) were noted. To date, two clinical studies of CCP-020 have been completed in patients with epidermolysis bullosa simplex (EBS). These include a Phase one pilot study in five patients and a Phase 2, multiple-site study in 17 patients in Europe. The Phase 2 study demonstrated CCP-020 was well-tolerated and no treatment-related AEs were reported. The Investigator's Brochure should be consulted for summaries of the results of these studies.¹

This Phase 1 study will assess the irritation potential of CCP-020 (Diacerein 1%) topical ointment.

1.2. Rationale for the Study

This study is intended to determine the contact sensitization (allergic) potential of topically applied CCP-020 (Diacerein 1%) topical ointment treatment on normal skin in healthy volunteers.

2. STUDY OBJECTIVES

The primary objective of this study will be to determine the potential of CCP-020 (Diacerein 1%) topical ointment to induce sensitization by repeated topical application to the healthy skin of humans under controlled conditions.

In addition, safety will be assessed by evaluation of any AEs reported during the study.

3. INVESTIGATIONAL PLAN

3.1. Study Design

This will be a randomized, single-center, controlled, evaluator-blinded, within-subject comparison study of the investigational products (IPs) (CCP-020 [Diacerein 1%] topical ointment and vehicle) and negative irritant control under occlusive conditions in healthy volunteer subjects. All subjects will have fields designated for the IP patches and the negative irritant control patch at 3 randomly assigned, adjacent sites, for the purpose of determining sensitization potential.

During the Induction Phase of the study, the IPs and negative irritant control will be applied to adjacent sites on the infrascapular area of the back. Evaluation of dermal reactions at the application sites will be assessed clinically using a visual scale that rates the degree of erythema, edema, and other signs of cutaneous irritation (see [Section 3.5.5](#)).

Following the Induction Phase, subjects will have a 10 to 14-day Rest Period, after which they will enter the Challenge Phase, which consists of one 48-hour patch application to a naïve site on the opposite side of the back. Observations based on the grading from [Table 3](#) at the naïve site during Challenge Phase and the patterns of reactivity during the Induction Phase will provide a basis for an interpretation of contact sensitization (see [Section 3.5.5](#)). Notations on the appearance of the skin will be made using the scoring system presented in [Tables 4 and 5](#).

If a cutaneous response observed in the Challenge Phase indicates possible sensitization (grade 3 or higher from [Table 3](#)), and/or at the discretion of the Investigator, a Rechallenge will occur (see [Section 3.5.1](#)). A narrative description of reactions in the Challenge and Rechallenge Phases will be reported together with the opinion of the Investigator as to whether such reactions are felt to be indicative of contact sensitization.

A total of 10 patch applications will be made over a period of approximately 6-8 weeks.

3.2. Discussion of Design

Allergic contact dermatitis (ACD), also referred to as dermal sensitization, is a delayed-type hypersensitivity reaction induced by small reactive chemicals (haptens).² It is a T-cell-mediated skin inflammatory systemic reaction, caused by repeated skin exposure to contact allergens. Erythema, edema, and occasionally papules and vesicles characterize the clinical appearance of this reaction. The ACD inflammatory skin reaction occurs as a delayed response (24-48 hours or longer) after contact with a sensitizing chemical.

In pharmaceutical and cosmetic industries it is mandatory to identify chemicals that are potential ACD inducers before they become a part of a new product.² Substances that come into contact with human skin need to be evaluated for their propensity to irritate and/or sensitize. Once an appropriate pre-clinical safety evaluation has been performed, a reproducible, standardized, quantitative patch evaluation procedure must be used to demonstrate that a particular material can be applied safely to human skin without significant risk of adverse reactions.³

Repeated insult patch test (RIPT) evaluation is a predictive patch study that can detect weak sensitizers that require multiple applications to induce a T-cell-mediated (Type IV) immune response sufficient to cause an allergic reaction. Irritant reactions may also be detected using this evaluation method, although this is not the primary purpose of this procedure.

The human RIPT study design is based on the Modified Draize procedure, and is an accepted standard methodology used for assessment of skin sensitization.^{4,5}

The IPs in the study will be CCP-020 (Diacerein 1%) topical ointment and Vehicle. The negative irritant control field will be 0.9% saline, 0.2 mL, applied topically under occlusive conditions.

3.3. Study Population

3.3.1. Subject Population

A sufficient number of subjects will be enrolled in order to provide 200 completed subjects evaluable for analysis; an individual subject will be allowed to participate in the study one time only.

A rationale for the choice of sample size is provided in [Section 4.2](#) of this protocol.

3.3.2. Inclusion and Exclusion Criteria

Inclusion Criteria

A subject will be considered eligible for participation in the study if all of the following inclusion criteria are satisfied prior to randomization:

1. Is a healthy male or female (to be confirmed by medical history);
2. Is 18 years of age or older;
3. In the case of a female of childbearing potential, is using two acceptable forms of birth control (oral/implant/injectable/transdermal contraceptives, intrauterine device, condom with spermicide, diaphragm with spermicide, abstinence, partner's vasectomy, tubal ligation). Abstinence or vasectomies are acceptable if the female subject agrees to implement two of the other acceptable methods of birth control if her lifestyle/partner changes;
4. In the case of a female of childbearing potential, has a negative urine pregnancy test (UPT) on Day 1 prior to randomization and are willing to submit to a UPT at the end of study (EOS);
5. Is free of any systemic or dermatological disorder, which, in the opinion of the Investigator, will interfere with the study results or increase the risk of AEs;
6. Is of any Fitzpatrick Skin Type or race, providing the skin pigmentation will allow discernment of erythema (see [Table 1](#));
7. Complete a medical screening procedure; and
8. Read, understand, and sign an informed consent.

Exclusion criteria

A subject who has any of the following will be excluded from the study:

1. Has any visible skin disease at the application site which, in the opinion of the Investigator, will interfere with the evaluation of the test site reaction;
2. Is using systemic/topical corticosteroids within 3 weeks prior to and/or during the study, or systemic/topical antihistamines 72 hours prior to and during the study;
3. Is not willing to refrain from using systemic/topical anti-inflammatory analgesics such as aspirin (81 mg daily aspirin will be allowed), Aleve, Motrin, Advil, or Nuprin for 72 hours prior to and during the study (occasional use of acetaminophen will be permitted);
4. Is using medication which, in the opinion of the Investigator, will interfere with the study results (e.g. anti-inflammatory medications, antipsychotics, anticonvulsants with potential pain relief effects, immunomodulatory medications, and others);
5. Is unwilling or unable to refrain from the use of sunscreens, cosmetics, creams, ointments, lotions or similar products on the back during the study;
6. Has psoriasis and/or active atopic dermatitis/eczema;
7. Has a known sensitivity or allergy to constituents of the materials being evaluated including diacetin, mineral oil, petrolatum, cetyl alcohol, D&C Yellow #10 and/or ethyl paraben;
8. Is a female who is pregnant, plan to become pregnant during the study, or is breast feeding a child;
9. Has damaged skin in or around the test sites, including sunburn, excessively deep tans, uneven skin tones, tattoos, scars, excessive hair, numerous freckles, or other disfigurements of the test site;
10. Has received treatment for any type of internal cancer within 5 years prior to study entry;
11. Has a history of, or are currently being treated for skin cancer and/or hepatitis;
12. Has a history of, or is currently being treated for, insulin dependent diabetes;
13. Has any condition that might compromise study results;
14. Currently or expect to sunbathe or use tanning salons during the study;
15. Is currently participating in any clinical testing;
16. Has any known sensitivity to adhesives; and/or
17. Has received any investigational drug(s) within 4 weeks prior to study entry.

3.3.3. Interruption or Discontinuation of Treatment

In accordance with legal requirements and ICH-GCP guidelines, every subject or his/her legal representative has the right to refuse further participation in the study at any time and without providing reasons (see also [Section 5.3](#)). A subject's participation is to be terminated

immediately upon his/her request. The Investigator should seek to obtain the reason and record this on the case report form (CRF).

If at the time of refusal a study product has already been administered, the subject should be advised on follow-up safety investigations. If a subject withdraws from the study, all efforts will be made to complete a final evaluation if possible. Subjects discontinued for having experienced an AE will be followed until the AE is resolved, a reasonable explanation is provided for the event, or the subject is referred to his/her own primary medical doctor (PMD). The specific AE in question will be recorded on the appropriate CRF.

If a subject develops a serious adverse event (SAE), his/her termination from the study will be considered by the Investigator. Similarly, if the subject develops conditions over the course of the study which would have excluded his/her entry in the study according to the safety-related medical exclusion criteria, he/she must be withdrawn immediately.

The subject may be withdrawn from the study at any time at the discretion of the Investigator for medical reasons and/or due to non-adherence to the treatment scheme and other duties stipulated in the study protocol. The reasons are to be documented on the CRF.

Individual patches may be discontinued if a reaction of a grade of 3 or greater (see [Section 3.5.5](#) for examples of values using additive grades from [Tables 3](#) and [Table 4](#)) occurs at any point during the study. Further patch applications of that product on that individual subject will be terminated. A “not patched” (NP) symbol and a score of 3 will be assigned for all subsequent days.

If a reaction is observed in any induction evaluation, a change in site location for the remaining applications in the Induction Phase will take place for that particular patch. See [Section 3.5.5](#) for interpretations of scores.

In addition, the Sponsor retains the right to end the study at any time if the study cannot be carried out as agreed upon in the protocol. In case of premature termination or suspension of the study, the Sponsor’s study manager will promptly inform the Investigator/institutions and regulatory authorities of the termination or suspension and the reason for that. It is the responsibility of the Principal Investigator (PI) to notify the Institutional Review Board (IRB) in the case of premature termination/suspension.

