Subjects who are absent once during the 3-week, 9-patch Induction Phase will be instructed to keep the patches in place and return to the facility on their next scheduled visit. They will be scheduled to receive a make-up (MU) patch application at the last Induction visit. The MU patches will be removed 48 – 72 (\pm 4) hours later and the sites will be graded. If subjects fail to return for removal/evaluation of the MU patch, a no ninth grading (N9G) will be recorded.

In cases where the subject misses the 9th evaluation in Induction Phase, the subject will be allowed to remove the patches by themselves in accordance with investigative personnel instructions. A telephone log will be written for any subjects that experience this situation to document the telephone conversation regarding the removal by subject.

Subjects who miss the 9th evaluation, but have had 9 patch applications will be considered to have completed the Induction Phase.

During Induction, the actual patch test grade is a combination of a numerical ([Table 3](#)) and letter ([Table 4](#)) grade consistent with the definitions given in the grading scales. A grade of 3 or higher to a specific study material (see [Section 3.5.5](#) for interpretation of symbols) observed at the first or second reading of the Induction Phase would indicate the subject is pre-sensitized, and application of the product(s) in question would be discontinued. If these reactions are observed after the first or second reading of the Induction Phase, this would necessitate a change in patch location to a naïve site. A second site change to the specific study material would potentially require a patch condition change to semi-occlusive conditions for the remaining applications in the Induction Phase (see [Section 3.5.6](#)).

Rest Period

During the Rest Period of approximately 10-14 days, subjects will not receive any application of study materials.

Challenge

At the Challenge Phase, subjects who have completed the Induction Phase and the Rest Period will have identical patches applied to naïve sites. Patches will remain on the naïve sites for 48 (\pm 1) hour to be evaluated at 30 (+ 10) minutes and 24 (\pm 1), 48 (\pm 1), and 72 (\pm 4) hours following patch removal (e.g., apply patch on Monday, remove patch on Wednesday, evaluate

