3.5.6. Criteria for Changing the Application Site or Conditions

A grade of 3 or higher to a study product (using [Table 3](#) and [Table 4](#)) observed at the first or second reading of the Induction Phase would indicate the subject to be pre-sensitized, and application of the product in question would be discontinued.

After the second reading of the Induction Phase, reactions graded 3 or higher (using [Table 3](#) or [Table 4](#)) require that the investigational product be applied to a naïve site under occlusive conditions. Such a change of application site may occur no more than twice during the Induction Phase for a particular product, after which applications of the product will be discontinued for that subject for the remainder of the study. Subjects requiring site changes due to irritancy in the Induction Phase will be considered evaluable for sensitization, provided that they receive a total of no fewer than 9 applications of the product.

No more than 2 changes for a given product will occur, whether the changes are to a new site under occlusive conditions (first move) or a new site under semi-occlusive conditions (second move).

Occlusive patch conditions include a Webril® cotton patch surrounded with Blenderm tape and covered with paper tape. There is no air flow under the patch. Semi-occlusive patch conditions include a Webril® cotton patch covered with paper tape, to allow air flow under the patch itself.

The 3-week period of continuous patch contact during the Induction Phase frequently results in tape-related irritation that is exacerbated by warm weather, but which occurs among some individuals irrespective of the season. Since adhesive tape is an integral part of the test article, tape-related irritation at the site will be documented as an application site reaction using the symbol “T” from [Table 5](#). Severe tape-related irritation will require a change of application site. Mild and moderate tape related reactions will not require of a change of application site. If all sites are experiencing tape reactions, the patch sites will be discontinued and a not patched (NP) symbol will be recorded for the remainder of the study. The subject will be discontinued from the study. An AE will be recorded in order to follow through to resolution of the tape related reaction.

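### For an Induction score of 3 or more after reading 2, protocol 3.3.3 permits stopping the product while 3.5.1 and 3.5.6 require moving it, and the choice decides who can be assessed for sensitization

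*Combined protocol and SAP*

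**What the plan says.** Section 3.3.3 states a general stopping rule: "Individual patches may be discontinued if a reaction of a grade of 3 or greater" occurs, at any time in the study. It continues: "Further patch applications of that product on that individual subject will be terminated". The subject is then coded NP and given a score of 3 on every later day. The next paragraph of 3.3.3 gives a different instruction, without a threshold: "If a reaction is observed in any induction evaluation, a change in site location" follows for the remaining Induction applications.

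Sections 3.5.1 and 3.5.6 split the rule by reading. According to 3.5.1, a grade of 3 or more "observed at the first or second reading of the Induction Phase would indicate the subject is pre-sensitized", and the product is stopped. If the reaction comes later, "this would necessitate a change in patch location to a naïve site". Section 3.5.6 agrees: later reactions of that grade "require that the investigational product be applied to a naïve site under occlusive conditions". It sets a limit: "Such a change of application site may occur no more than twice during the Induction Phase for a particular product". Subjects who were moved "will be considered evaluable for sensitization, provided that they receive a total of no fewer than 9 applications of the product".

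Under 3.5.1 (Challenge), a completed case has 9 Induction applications with at least 8 readings, plus one Challenge application with 4 readings, and only completed cases are used to assess sensitization. Section 4.3 instead bases that assessment on everyone who completes Challenge. Section 3.3.1 plans enrolment so as to yield 200 completed, evaluable subjects. Section 4.2 gives a 1.5% upper bound if none of them reacts.

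**The concern.** One trigger carries a permitted stop in one section and a mandatory move in two others, and nothing says how staff should choose. At readings 1 and 2 the conflict takes another form: the second paragraph of 3.3.3 would move a product that 3.5.1 and 3.5.6 stop.

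The choice matters for the primary objective. Section 4.6.2 rests the formal determination of sensitization on Challenge, confirmed at Rechallenge if necessary, and section 4.1 treats a single sensitization reaction as enough to suggest hypersensitivity potential. A subject whose product was stopped in Induction has no Challenge patch for it and cannot supply that reaction. The subjects at risk of removal are those with strong Induction reactions. Table 3 grades of 3 and above include papules, edema and vesicles, which section 3.2 also names as features of allergic contact dermatitis. Some such scores will be plain irritation. The plan relies on Challenge to tell the two apart.

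**Working it through.** **The plan's own figure.** The inputs are 0 reactions, 200 evaluable subjects and 95% confidence (section 4.2). The one-sided exact bound is 1 − 0.05^(1/200) = 0.01487, or 1.49%. The rule of three gives 3/200 = 1.5%. The stated 1.5% is reproduced and is not in dispute.

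**The instructions side by side, for a score of 3 or more.**

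| Induction reading | 3.3.3, stopping paragraph | 3.3.3, next paragraph | 3.5.1 and 3.5.6 |
|---|---|---|---|
| 1–2 | stop permitted | move | stop |
| 3–9 | stop permitted | move | move, at most twice |

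Neither row has one action across all three columns.

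**Applications under a stop.** With no missed visit, r applications have been made by reading r.
- A stop at r = 3, 4, 5, 6, 7 or 8 leaves 3, 4, 5, 6, 7 or 8 applications. All are below the 9 required.
- A stop at r = 9 leaves 9 applications. But 3.3.3 ends all further applications of the product, so there is no Challenge patch and none of the 4 Challenge readings.
- The subject is therefore a completed case for that product in 0 of the 7 positions.

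**Applications under a move.** I read the two-move limit in 3.5.6 together with 3.5.1, where the second move continues patching for the remaining Induction applications. A third score of 3 or more then ends the product.
- With one such score at readings 3–9, the subject can stay evaluable in 7 of 7 positions.
- With two such scores, the subject can stay evaluable in all 7 × 6 / 2 = 21 pairs of positions.
- A third such score can come no earlier than reading 5 (readings 3, 4 and 5).

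**Effect on the bound.** With enrolment planned to deliver 200 completed subjects, 0 in 200 gives 1.49% whatever the number stopped. Precision is not the issue. If, purely for illustration, 5 or 20 of the 200 were lost and not made up, the bound would be 1 − 0.05^(1/195) = 1.525% or 1 − 0.05^(1/180) = 1.651%. What changes is whom the figure describes.

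**Unit of evaluability.** The count above is per product. Section 3.5.6 suggests that unit by requiring 9 applications of the product. Section 3.5.1 defines a completed case per subject, so a subject stopped on one of three products might be incomplete altogether. Under 4.3, a subject stopped on CCP-020 but challenged with vehicle and saline might count as having completed Challenge without any CCP-020 Challenge reading. The documents do not say which applies.

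**The case against.** The strongest reply is that there is no head-on collision. Section 3.3.3 says patches *may* be discontinued, and the sentence on termination can be read as what follows once that option is taken. The next paragraph of 3.3.3 itself points to a site change, and 3.5.6 is the dedicated section. This stands in part: it is a permissive general rule beside a mandatory specific one. A reader might infer that the protocol orders both a stop and a move for every such reaction, and the word *may* does not support that. But an optional stop is still incompatible with a required move, and no criterion governs the option.

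Three other inferences go further than the documents:
- **That sensitization is judged from Challenge alone.** Section 3.1 also uses Induction reaction patterns in interpreting contact sensitization. They are supporting information. They do not replace the Challenge reaction on which 4.6.2 bases its determination.
- **That stopped subjects are replaced under a stated rule.** Section 3.3.1 says only that enough subjects will be enrolled to give 200 completed ones. Over-enrolment at the start fits equally well.
- **That the number stopped would be lost.** It could be recovered from the NP codes (3.3.3), the patch records on the CRF (3.4.7) and the compliance summary (4.3.2). What is missing is any link to the sensitization result.

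It is also fair to say that the position counts restate the rules and do not measure impact. The documents give no rate of such reactions.

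**Conclusion.** The inconsistency is real and touches the primary assessment. After reading 2, the same reaction can end a product under 3.3.3 or keep it going under 3.5.1 and 3.5.6. A stop costs completed-case status for that product at every one of readings 3 to 9, while a move can preserve it. At readings 1 and 2, the second paragraph of 3.3.3 conflicts with the stop in 3.5.1 and 3.5.6.

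This rests on three assumptions: no missed visit, evaluability judged per product, and the reading of the two-move limit given above. A reader might go on to infer that the 1.5% bound is wrong or that a sensitizer would be missed. The bound is correct for the subjects it covers. The documents give neither the number who would be stopped nor their chance of sensitization, so no loss of detection can be calculated. The supportable conclusion is narrower: a 0-in-200 result would describe only subjects who were not stopped, and the plan does not require that to be shown. It should be fixed.

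**What to change.** 1. Amend 3.3.3, 3.5.1 and 3.5.6 so that one action applies at each Induction reading. Which action that is remains a clinical decision for the sponsor and investigator. The SAP promised in 4.1 can settle reporting but cannot govern what site staff do, so this needs a protocol amendment.
2. In the same amendment, give one definition of the sensitization population across 3.5.1, 3.5.6 and 4.3, and state whether it applies per product or per subject.
3. In 4.6.2, add a listing by product, placed beside the sensitization result, of subjects stopped for a score of 3 or more who did not reach Challenge, with their Induction scores. State that the upper bound excludes them.

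The cost is one amendment and one listing from data already collected. No new assessments or extra analyses are needed.
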